The Time to Recurrence is defined as time from Day 1 Treatment to the date of the first histologically confirmed recurrence (using the date of corresponding cystoscopy) of the patient's bladder tumor. Patients without recurrence at the time of the primary analysis will be censored at the last available date of cystoscopy. Patients who died due to any cause before confirmed recurrence will be censored at the last available date of cystoscopy.

The following sensitivity analyses will be performed for the primary analysis.

1. Analysis of time to recurrence by excluding patients who miss 2 consecutive cystoscopies or lost to follow-up either prior to recurrence or prior to the date of the primary analysis – Completer analysis
2. Analysis of time to recurrence by excluding patients who miss 2 consecutive cystoscopies or lost to follow-up either prior to recurrence or prior to patient's follow-up duration of 24 months – Completer 24 Month analysis
3. Analysis of time to recurrence by considering patients with no recurrence who miss 2 consecutive cystoscopies or lost to follow-up prior to date of the primary analysis as recurred.

The primary analysis will be conducted using a hierarchical procedure of hypothesis testing at a 5% level of significance. The primary endpoint, Time to Recurrence, will be examined first, and if significant, the secondary endpoint, 2-Year Recurrence Rate, will be examined next, and if also significant, Extent of Disease at Recurrence, and Time to Disease Progression will then be examined in that order.

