Once randomized, patients will undergo TURBT on Day 1 and the study drug instillation will occur at 60 ± 30 minutes post-TURBT and will be retained for 60 minutes (± 5 minutes) in the bladder. All histology specimens will be reviewed by a local pathology laboratory and all clinical treatment decisions will be based on the local pathology review. Patient target disease will be confirmed and efficacy analyses will be performed based on the pathology results. The target study population is low- to intermediate-risk patients who have Ta histology, including PUNLMP, as confirmed by a pathology laboratory. Patients whose tumor histology does not meet the criteria for eligibility, as confirmed by pathology (Non-Target Population), will be followed up for safety on Day 35 (± 5 days) (Safety Follow-up Visit) and will then be discontinued from the study. If the pathology results are delayed beyond 35 days, the Safety Follow-up Visit will be conducted when the results are available for these patients.

Patients who have pathology confirmed target histology will not receive additional treatment for NMIBC during the follow-up prior to recurrence. All patients will be followed until either a confirmed tumor recurrence or the End-of-Study, whichever occurs first.

The primary analysis will be conducted once the required number of recurrence events are observed as detailed in the Statistical Methods below. The number of events needed to perform the final primary endpoint analysis was estimated based on the recurrence rate at 24 months from previous studies. The follow-up schedule is below:

- Cystoscopic examination and urine cytology every 3 months (± 30 days) (calculated from date of TURBT) for 2 years for tumor recurrence and progression and then every 6 months (± 60 days) until either a confirmed tumor recurrence or the End-of-Study, whichever occurs first.
- If at any time during the study there is a histologically confirmed tumor recurrence, the patient will be discontinued from the study at that time and may then be treated per the Investigator's standard of care.

The study will end (End-of-Study) when the required number of events for the primary endpoint analysis are accrued.

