4.3 Patient Discontinuation/Withdrawal Criteria

Patients can withdraw from participation in this study at any time, for any reason, specified or unspecified, and without prejudice.

Patients must be withdrawn from study participation for the following reasons:

[figure not shown]
- It is determined by Day 1 pathology review that the patient has histology other than low-to intermediate-risk NMIBC
- Development of an adverse event (AE) that interferes with the patient's participation
- Patient withdrawal of informed consent
- Investigator decision
- Sponsor decision
- The patient refuses further follow-up study procedures, including cystoscopy
- The patient is lost to follow-up (missed at least two consecutive follow-up cystoscopies)
- Patient has a cystectomy
- Patient has a histologically-confirmed recurrence
- Death
- Pregnancy

The reason for the patient discontinuing study treatment or terminating from the study must be recorded on the case report form (CRF). For patients who discontinue from the study during the follow-up period or who are withdrawn, the date of last contact will be the final visit.

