5.4.8 Cystoscopy

Cystoscopy will be performed at Screening (or up to 45 days prior to signing of informed consent), every 3 months (± 30 days) from the date of TURBT for the first 2 years, and every 6 months (± 60 days) until either a confirmed tumor recurrence or the End-of-Study, whichever occurs first. An operative report should contain the number, size and location of the tumors. All lesions should be biopsied and sent for pathological review; recurrences are to be reported on the appropriate CRF. All clinical decisions will be made based on the local pathologist's report. All pathology reports must include the tumor stage and grade for each lesion removed.

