7.3.1 Recording of Adverse Events

From the time the study Informed Consent is signed through the day of study drug administration, only SAEs that are related to study procedures are to be recorded. For all non-Target population patients, all adverse events from the time of study drug administration until Day 35 (± 5 days) post-TURBT will be recorded. For Target population patients, all adverse events will be recorded from the time of study drug administration until the 3-month Follow-up Visit. Only AEs related to study procedures and deaths will be recorded from the 3 month visit until a recurrence or the remainder of the follow-up period, whichever comes first.

All AEs should include resolution at the End-of-Study for a patient. The following conventions should be followed when patient completes or discontinues from the study

- If a patient dies, the date of death should be the date of AE stop for all ongoing AEs at the time of death.
- If a patient discontinues study drug due to an AE(s), the outcome of the AE is to be followed for 35 days (± 5 days) from the date of discontinuation or until the AE has returned to Grade ≤ 1 or returned to baseline conditions for the patient.

The status of the AE and the date of last contact with the patient will be captured. If the AE has not returned to Grade ≤ 1 or to Baseline conditions for the patient by the End-of-Study, the AE stop date should be left as ongoing.

All AEs will be classified by intensity/severity ([Section 7.3.2](#)), relationship to study drug ([Section 7.5](#)), and as serious or nonserious ([Section 7.7](#)).

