8.5.5 Primary Endpoint - Time to Recurrence

The Time to Recurrence is defined as time from Day 1 treatment to the date of the first histologically confirmed recurrence as described in [Section 8.5.1](#) above. Patients without a recurrence at the time of the primary analysis will be censored at the last available date of cystoscopy. Patients who died due to any cause before confirmed recurrence will be censored at the last available date of cystoscopy.

The primary analysis will be conducted using a hierarchical procedure of hypothesis testing at a 5% level of significance. The primary endpoint, Time to Recurrence, will be examined first, and if significant, the secondary endpoint, 2-Year Recurrence Rate, will be examined next, and if also significant, Extent of Disease at Recurrence, and Time to Disease Progression will then be examined.

The primary endpoint of Time to Recurrence will be analyzed using the Target Population as defined in [Section 8.3](#). The primary analysis of Time to Recurrence will be conducted once a total of 208 recurrence events are accrued in the study. The primary endpoint analysis involves a 2-sided log-rank test of time to recurrence between two treatment groups at 5% level of significance. Distribution of Time to Recurrence will be estimated using the Kaplan-Meier product-limit method. The median times to recurrence with two-sided 95% confidence intervals (CI) will be estimated, together with the estimates at 6, 12, 18 and 24 months. The hazard ratio and corresponding 95% CI of the treatment effect will be estimated from a Cox proportional hazard regression model with treatment arm as the only covariate and tested using a likelihood ratio test at the level of significance described above. Additional exploratory analysis of Cox proportional hazard regression will be used to estimate the hazard ratio and its 95% CI. The model will include treatment effect, study center, low vs intermediate risk, primary vs. recurrent disease as stratification factor in addition to any other baseline or demographics factors.

In addition, the following additional sensitivity analyses of Time to Recurrence will be provided:

- a. Excluding patients who miss 2 consecutive cystoscopies or lost to follow-up either prior to recurrence or prior to the date of the primary analysis – Completer analysis

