8.5.6.3 Time to Disease Progression

Time to Progression is the time from Day 1 to the first documentation of stage progression as confirmed by pathology. Only the development of $\geq T2$ disease will be included in the assessment of time to disease progression. Censoring of patients with no documented progression will be the same as described for recurrence in [Section 8.5.5](#) above.

Distribution of Time to Progression will be estimated using the Kaplan-Meier method. Analysis of Time to Progression will be similar to the analysis of Time to Recurrence, above.

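### Protocol only: Time to Disease Progression can record only T2-or-worse disease at first recurrence, and its Kaplan-Meier curve overstates how often that happens

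*Protocol*

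**What the plan says.** **Definitions.** Protocol Section 8.5.4 defines recurrence as any pathologically confirmed disease of Ta or worse, or CIS, after treatment, and progression as confirmed T2 or worse. Section 8.5.6.3 repeats that only T2-or-worse "disease will be included in the assessment of time to disease progression". Section 2.2 lists the endpoint as a secondary objective.

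**End of observation.** Section 3.1 provides that if at any time "there is a histologically confirmed tumor recurrence, the patient will be discontinued from the study at that time". The mandatory withdrawal reasons in Section 4.3 include "Patient has a histologically-confirmed recurrence". Section 5.4.8 schedules cystoscopy "until either a confirmed tumor recurrence or the End-of-Study, whichever occurs first". No section arranges staging after a recurrence.

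**Analysis.** Section 8.5.6.3 says "Censoring of patients with no documented progression will be the same as described for recurrence in" Section 8.5.5, that is, at the last available cystoscopy. It specifies Kaplan-Meier estimation and otherwise follows the Time to Recurrence analysis (log-rank and Cox).

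**Hierarchy.** After Time to Recurrence and 2-Year Recurrence Rate, the Synopsis (Statistical Methods) states that "Extent of Disease at Recurrence, and Time to Disease Progression will then be examined in that order". Section 8.5.5 gives the same sequence. Section 8.5.6.2 limits Extent to patients with recurrence and describes it by quantiles, counts, percentages and discordance rates, with no test.

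**SAP.** SAP 1.0 removes every efficacy objective, endpoint and analysis after early termination (Summary of Changes; Sections 3.4.1 and 6).

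**The concern.** Time to progression is ordinarily understood to cover a patient's course up to muscle-invasive disease, including progression that follows one or more lower-stage recurrences. Here the follow-up rule removes that route. A patient whose first recurrence is Ta, T1 or CIS leaves the study and is censored as having no documented progression. What remains is the stage of the first recurrence, together with its date.

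Three things follow. The Section 2.2 objective cannot be met as labelled, and no analysis plan could recover stages that were never collected. The Kaplan-Meier curve treats patients who have left with a lower-stage recurrence as if they could still have a T2-or-worse first recurrence, so it overstates how often that event occurs. And the step before it in the testing sequence, Extent, has no stated pass rule.

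**Working it through.** **Step 1: logic.** T2 or worse is contained in Ta or worse, so every progression is also a recurrence. Observation ends at the first confirmed recurrence. Hence the progression date equals the first-recurrence date for every countable progression. T2 found on resection of that same recurrence is still first-recurrence disease.

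**Step 2: reproduce the plan's event count.** Inputs from Section 8.1: placebo hazard 0.3 (read as per year), HR 0.65, so Qapzola hazard 0.3 × 0.65 = 0.195; 141 and 284 patients; 24 months' accrual (taken as uniform) plus 24 months' follow-up. With exponential times,

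P = 1 − [exp(−2L) − exp(−4L)] / (2L)

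- Placebo: P = 0.5873; 0.5873 × 141 = 82.8
- Qapzola: P = 0.4394; 0.4394 × 284 = 124.8
- Total 207.6, against 208 stated. The figure reproduces.

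**Step 3: follow-up that is not observed.** Mean available follow-up is 3 years and mean time to recurrence or end is P/L, so a patient who recurs would on average have had (3 − P/L)/P more years before End-of-Study:

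- Placebo: (3 − 1.958)/0.5873 = 1.77 years
- Qapzola: (3 − 2.253)/0.4394 = 1.70 years

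Progression in that time is not seen. This needs no assumption about stage.

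**Step 4: Kaplan-Meier against cumulative incidence at 24 months.** Let s be the share of first recurrences that are T2 or worse. The documents do not give it. I assume 1% to 10%, constant over time and equal in both arms.

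- 1 − KM, lower-stage recurrences censored: 1 − exp(−2sL)
- Cumulative incidence: s × [1 − exp(−2L)], where 1 − exp(−2L) is 45.1% (placebo) and 32.3% (Qapzola)

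| s | Placebo: 1−KM / cum. inc. | Qapzola: 1−KM / cum. inc. | Arm difference (points): 1−KM / cum. inc. | Gap (points) |
|---|---|---|---|---|
| 1% | 0.598% / 0.451% | 0.389% / 0.323% | 0.209 / 0.128 | 0.08 |
| 2% | 1.193% / 0.902% | 0.777% / 0.646% | 0.416 / 0.256 | 0.16 |
| 10% | 5.824% / 4.512% | 3.825% / 3.229% | 1.999 / 1.282 | 0.72 |

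In relative terms the overstatement is about 29% to 33% in placebo and 18% to 21% in Qapzola, on small absolute risks. Event counts are s × 207.6: about 2, 4 and 21. Between 187 and 206 patients would leave with a lower-stage recurrence.

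**Step 5: death before recurrence as a further competing event.** Section 1.3.2 reports about 3% of patients with fatal adverse events over roughly 2 years in the earlier studies. Assuming this carries over, m = 0.015 per year and cumulative incidence is s × L/(L + m) × [1 − exp(−2(L + m))]. The gap in the arm difference becomes 0.08 to 0.73 points, almost unchanged.

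**Step 6: the hazard comparison.** With s equal in both arms, the cause-specific HR is (s × 0.195)/(s × 0.3) = 0.65, identical to the recurrence HR. The endpoint can depart from the recurrence result only through a difference in stage mix at first recurrence.

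**The case against.** The strongest reply is that nothing practical depends on this. SAP 1.0 drops all efficacy analyses, progression was last in the sequence, and the primary test and its 5% level are untouched. That stands and is why the point is minor in practice.

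The exit rule can also be defended. After recurrence, treatment follows the investigator's standard of care (Section 3.1), so stopping there keeps later therapy out of the comparison. That justifies the rule, but not the label. Section 8.5.6.3 is open that only T2 or worse counts; it does not say that only first recurrences can count.

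The size rests on an unsourced T2 share, and the absolute differences are small. That is also fair. The structural gap in Steps 1 and 3 does not depend on the share. The count in Step 2 and the times in Step 3 use the 24 + 24 months of Section 8.1; the Synopsis and Section 3.2 also give 2.5 + 2.5 years, which at the same hazards would yield about 240 events if follow-up did not stop at 208. The 24-month figures in Step 4 do not depend on either.

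A reader might infer more than the documents support:

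- *That the log-rank or Cox result is invalid.* It remains a valid comparison of the cause-specific hazard of T2-or-worse first recurrence.
- *That Extent could never serve as a step in the sequence.* Sections 8 and 8.4 defer detail to an SAP, which could have added a test, and a test among patients with recurrence can give a valid p-value for its conditional null. It would compare subsets formed after randomization and lack a clean causal reading.
- *That deaths and adverse events also go unrecorded after recurrence.* Section 7.3.1 says that these "will be recorded from the 3 month visit until a recurrence or the remainder of the follow-up period, whichever comes first", but Sections 5.4.10 and 7.2 and schedule footnote j run the recording to End-of-Study. The documents conflict, and the argument does not need the point.

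**Conclusion.** The point holds for the protocol. As designed, Time to Disease Progression measures time to a T2-or-worse first recurrence, and the objective in Section 2.2 cannot be met under its present name. The hazard comparison is sound for that narrower event; the Kaplan-Meier estimate of its frequency is biased upward. At an assumed 2% share the bias is 1.19% against 0.90% in placebo at 24 months and 0.16 points on the arm difference; across 1% to 10% the shift is 0.08 to 0.72 points. These figures rest on exponential hazards of 0.3 and 0.195 per year and a T2 share that is constant and equal between arms. Measured against all progression, including later cases never collected, the direction of error is unknown.

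Extent, as written, supplies no pass rule for the step that follows it. No reported result is affected, because SAP 1.0 contains no efficacy analysis.

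**What to change.** Rename the endpoint *muscle-invasive (T2 or worse) disease at first recurrence* in Protocol Sections 2.2, 8.5.3 and 8.5.6.3 and in the matching Synopsis entries.

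In Section 8.5.6.3, replace the Kaplan-Meier estimate with cumulative incidence by arm. Treat non-muscle-invasive recurrence (Ta, T1, CIS), death before recurrence, and cystectomy without confirmed recurrence (a withdrawal reason in Section 4.3) as competing events. State how patients withdrawn for other bladder cancer therapy (Synopsis; Section 6.7.2) are handled. Keep the cause-specific hazard ratio as supportive.

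Report Extent descriptively rather than as a gate. Time to Recurrence followed by 2-Year Recurrence Rate then forms the tested sequence.

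The cost is protocol wording and the loss of a formal progression or extent claim; SAP 1.0 has no efficacy text to change. If the sponsor wants to keep the objective under its present name, the optional and costlier alternative is to collect pathology stage after recurrence until End-of-Study. That adds follow-up for about 208 patients, with later staging obtained after investigator-chosen treatment.

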3.2 Study Duration

The estimated duration of the study is approximately 5 years (2.5 years accrual + approximately 2.5 years follow-up).

The total duration of the study for each patient will be approximately 5 years including:

- **Screening Period:** up to 30-days
- **Treatment:** Day 1
- **Safety Follow-up:** Day 35 (± 5 days) (non-Target Population) or Month 3 Follow-up Visit (Target Population)
- **Follow-up Period:** No follow-up in non-Target Population. Until either a confirmed tumor recurrence or the End-of-Study, whichever occurs first in Target Population.

4 PATIENT POPULATION

4.1 Inclusion Criteria

1. Patient must have a clinical diagnosis of low- to intermediate-risk non-muscle invasive bladder cancer according to the 2016 American Urological Association (AUA) Guidelines
2. Patient must be willing to give written informed consent and must be able to adhere to dosing and visit schedules, and meet all study requirements.
3. Patient is at least 18 years of age and <90 years of age at the time Informed Consent is signed.
4. Patient must be willing to practice two forms of contraception, one of which must be a barrier method, from study entry until at least 35 days after study treatment. Patients surgically sterilized or who are postmenopausal for at least 1 year (defined as more than 12 months since last menses) do not require contraception.
5. Females of childbearing potential must have a negative pregnancy test within 30 days prior to randomization. Females who are postmenopausal for at least 1 year (defined as more than 12 months since last menses) or are surgically sterilized do not require this test.

4.2 Exclusion Criteria

1. Patient has malignancy or life-threatening systemic disease or a history of advanced, serious, life-threatening malignancy/disease within the last 5 years, except very low-risk prostate cancer
2. Patient has used any investigational drugs, biologics (vaccines, antibodies), or devices within 30 days prior to study treatment or has plans to use any of these during the course of the study
3. Patient has received any pelvic radiotherapy (including external beam and/or brachytherapy)
4. Patient has a history of allergy to red color food dye or any other component of Qapzola, placebo, or their diluents
5. Patient has had a surgical procedure 4 weeks prior to TURBT or will have other surgical procedures performed at the time of TURBT or within 4 weeks after TURBT
6. Patient has any unstable or uncontrolled medical condition that would make it potentially unsafe to undergo TURBT including a previous stroke or myocardial infarction within 6 months
7. Patient has an active uncontrolled infection, including a urinary tract infection, underlying medical condition, or other serious illness that would impair the ability of the patient to receive study treatment or undergo study procedures
8. Patient has a bleeding disorder or a screening platelet count $<100 \times 10^9/L$, or requires continuous anticoagulation or bridging anticoagulation during the procedure
9. Patient has a hemoglobin value <10 g/dL at Screening
10. Patient has ever had confirmed extravesical urothelial disease (upper tract and urethral including prostatic urethral)

11. Patient with a history of previous bladder cancer:
 - High-Risk NMIBC as classified per the 2016 AUA Guidelines
 - Bladder cancer that was muscle invasive or positive for lymph node or distant metastasis
12. Patient has received any previous intravesical therapy for bladder cancer- chemotherapy, immunotherapy, or previous exposure to Qapzola in the last 3 years
13. Patient has a tumor in the bladder diverticulum
14. Patient has a history of interstitial cystitis
15. Patient is pregnant or breast-feeding

4.3 Patient Discontinuation/Withdrawal Criteria

Patients can withdraw from participation in this study at any time, for any reason, specified or unspecified, and without prejudice.

Patients must be withdrawn from study participation for the following reasons:

[figure not shown]
- It is determined by Day 1 pathology review that the patient has histology other than low-to intermediate-risk NMIBC
- Development of an adverse event (AE) that interferes with the patient's participation
- Patient withdrawal of informed consent
- Investigator decision
- Sponsor decision
- The patient refuses further follow-up study procedures, including cystoscopy
- The patient is lost to follow-up (missed at least two consecutive follow-up cystoscopies)
- Patient has a cystectomy
- Patient has a histologically-confirmed recurrence
- Death
- Pregnancy

The reason for the patient discontinuing study treatment or terminating from the study must be recorded on the case report form (CRF). For patients who discontinue from the study during the follow-up period or who are withdrawn, the date of last contact will be the final visit.

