6.7.2 Prohibited Medications

Following Day 1 treatment and prior to recurrence, patients in the Target Population should not receive other medications to treat bladder cancer. If a patient starts another therapy for bladder cancer during the follow-up period, the patient will be withdrawn from the study.

No diuretics are allowed prior to instillation on study drug instillation day. Patients should have at least a 7- to 10-day washout period for all anticoagulants, including low-dose aspirin.

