8.1 Sample Size

The enrolled patients will be randomized in a 2:1 ratio to either Qapzola or placebo. The primary endpoint is Time to Recurrence in the Target Population. The primary endpoint analysis involves a test of comparison: 8 mg Qapzola vs. placebo using 2-sided log-rank test at 5% level of significance.

The sample size calculation assumes a hazard ratio (HR) of 0.65 based on the results from previous Phase 3 studies of Qapzola and placebo comparisons overall and in the drug instillation time window 31-90 minutes post-TURBT as described in [Section 1.3.1.2](#) and [Section 1.3.1.4](#) respectively.

Approximately 500 patients will be enrolled and treated in this study. Accrual time is estimated as 24 months and follow-up time as 24 months. For the sample size calculation, the HR of 0.65 is assumed for the improvement in time to recurrence in favor of Qapzola as compared to the Placebo with a hazard rate of 0.3. In a 2:1 randomization of Qapzola and Placebo, sample sizes of 425 Target disease patients (284 in Qapzola and 141 in Placebo) will provide 85% power. This sample size is estimated to provide a total of 208 recurrence events during the follow-up duration of at least 24 months. The sample size calculation was based on PASS 14 (NCSS, LLC, Kaysville, Utah).

Since the Target population is confirmed by pathology review and this will be performed after patients are randomized and have undergone TURBT procedure, the study will account for misclassification in the Target disease population. Accounting for 15% misclassification of randomized patients, the study will enroll approximately 500 patients. However, the study will continue to enroll patients until the required number of Target disease patients are accrued.

A futility analysis will be performed during the study conduct to determine the study continuation. The futility analysis will be conducted in the Target patients once 60 events are observed. The study will be stopped for futility if the calculated z-value from the log-rank test of HR is >1.0 . No adjustment for multiplicity of comparison will be made for futility analysis and the final analysis will be performed at 5% level of significance.

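### Mandatory withdrawal after two missed cystoscopies, or on starting other bladder cancer therapy, stops outcome collection in patients who could still be assessed, and other sections of the protocol point the other way

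*Protocol*

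**What the plan says.** Two protocol rules end follow-up early.

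- **Missed visits.** Section 4.3 lists reasons for which withdrawal is compulsory. One reads "The patient is lost to follow-up (missed at least two consecutive follow-up cystoscopies"). Consent withdrawal and refusal of further procedures are separate entries, so this one also reaches patients who have done neither. The same section makes the date of last contact the final visit. No later outcome collection is described.
- **Other therapy.** Section 6.7.2 states: "If a patient starts another therapy for bladder cancer during the follow-up period, the patient will be withdrawn from the study". The synopsis likewise ends follow-up at additional bladder cancer treatment. Other therapy is not among the compulsory reasons in Section 4.3.

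Other passages point the other way.

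- Section 3.1 follows all patients to confirmed recurrence or End-of-Study and does not mention other treatment as an end point of follow-up.
- In Section 8.5.5, sensitivity analyses (a) and (b) exclude patients who miss two consecutive cystoscopies or are lost to follow-up. Analysis (c) counts such patients as recurred if they have no recurrence. This wording separates missed visits from loss, and it allows that some patients who miss two visits have a recorded recurrence.

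For the primary analysis, "Patients without a recurrence at the time of the primary analysis will be censored at the last available date of cystoscopy". A rule that censors at the start of other therapy appears only under the exploratory per-protocol analysis.

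**The concern.** Treatment is one instillation on Day 1, so nothing about dosing requires observation to stop. Take a patient seen at month 3 who misses months 6 and 9. The attended visits would be 9 months apart if the patient came back at month 12. Under Section 4.3 the patient has already been withdrawn and would be censored at month 3, although the month 12 cystoscopy was scheduled and possible.

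Three things are at stake.

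- **Primary endpoint.** Temporary non-attendance becomes permanent censoring. If missing visits or starting other therapy is related to recurrence risk, the censoring is informative.
- **2-Year Recurrence Rate.** This is the first secondary endpoint in the testing hierarchy, and Section 8.5.6.1 defines it as a proportion with confirmed recurrence. It does not say how withdrawn patients count. If they stay in the denominator, they count as recurrence-free. The Kaplan-Meier estimate planned alongside would censor them instead.
- **Sensitivity analyses.** Two exclude the affected patients on the basis of behaviour after randomisation, and one imputes recurrence. None can use an outcome that was never collected, and none addresses other therapy.

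**Working it through.** **Inputs** (Section 8.1): "2-sided log-rank test at 5% level of significance"; hazard ratio 0.65 "as compared to the Placebo with a hazard rate of 0.3"; "sample sizes of 425 Target disease patients (284 in Qapzola and 141 in Placebo) will provide 85% power"; "Accrual time is estimated as 24 months and follow-up time as 24 months"; 208 events. The unit of the hazard is not stated. I take it as per year, which reproduces the stated events. The Qapzola hazard is then 0.65 × 0.3 = 0.195.

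**Step 1: reproduce the plan.** With uniform accrual over A = 2 years, minimum follow-up F = 2 years and withdrawal hazard w, the probability of an observed recurrence is

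p(λ) = λ/(λ+w) × {1 − [e^(−(λ+w)F) − e^(−(λ+w)(F+A))] / [(λ+w)A]}.

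With w = 0:

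- Placebo: 141 × 0.5873 = 82.8
- Qapzola: 284 × 0.4394 = 124.8
- Total: 207.6, which rounds to the stated 208

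Power by the Lachin-Foulkes formula at N = 425 is 85.2%, matching the stated 85%. The plan's figures therefore assume no loss to follow-up. Its only inflation is for non-target histology (425/0.85 = 500).

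**Step 2: total withdrawal.** The documents give no withdrawal rate. I assume a range, equal in both arms and unrelated to prognosis.

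| Withdrawal per year | Events at month 48 | Shortfall from 207.6 | Power at month 48 | Month when 208 is reached |
|---|---|---|---|---|
| 2% | 202.1 | 5.5 | 84.3% | about 50 |
| 5% | 194.3 | 13.3 | 83.0% | about 52 |
| 10% | 182.2 | 25.4 | 80.7% | about 58 |

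**Step 3: the avoidable part.** A patient who never returns is censored at the last cystoscopy under any rule. The withdrawal rules cost only the recurrences of patients who would return or could still be assessed. If a share r of withdrawals is recoverable, the avoidable loss is the event count at withdrawal hazard w(1−r) minus the count at w.

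| Withdrawal per year | r = 10% | r = 50% |
|---|---|---|
| 2% | 0.5 | 2.7 |
| 5% | 1.3 | 6.5 |
| 10% | 2.3 | 12.1 |

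For example, at 10% per year with half recoverable, the withdrawal hazard falls to 5% per year: 194.3 − 182.2 = 12.1 events.

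**Step 4: direction of bias.** One simulated data set of 400,000 patients with true hazard ratio 0.65 removed a share of recurrences by censoring each affected patient half a year before the recurrence.

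| Recurrences lost, placebo / Qapzola | Estimated hazard ratio | Events per 425 patients |
|---|---|---|
| 0% / 0% | 0.66 | 208.0 |
| 5% / 5% | 0.66 | 197.6 |
| 10% / 10% | 0.65 | 187.0 |
| 10% / 5% | 0.69 | 193.5 |
| 5% / 10% | 0.62 | 191.4 |
| 15% / 5% | 0.72 | 189.4 |
| 5% / 15% | 0.59 | 185.1 |

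The no-loss run gives 0.66 rather than 0.65 through simulation error. Equal loss leaves the ratio essentially unchanged; unequal loss moves it in either direction. The four unequal settings remove 14.5 events (208.0 − 193.5) to 22.9 events (208.0 − 185.1), which is more than the 12.1 at the top of Step 3. They show direction and overstate what the withdrawal rules alone would do.

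**The case against.** The strongest case on the other side has four parts.

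- **A returning patient's recurrence may count anyway.** A reader might infer from Section 4.3 that a recurrence found on return cannot be counted. The documents do not establish that. Section 8.5.5 counts the first histologically confirmed recurrence, Section 3.1 follows all patients, and the sensitivity analyses assume that some patients with two missed visits have recorded recurrences. This stands. What can be supported is that the sections conflict, and that sites following Sections 4.3 and 6.7.2 literally would stop collecting the data.
- **The event loss is small and already handled.** A reader might charge the whole shortfall of about 5 to 25 events in Step 2 to these rules, or conclude that the trial would be underpowered. Neither follows. Most of that loss may occur under any rule. The analysis waits for 208 events, and Section 8.1 allows added patients if recurrence is low. The synopsis and Section 3.2 also plan about five years (2.5 + 2.5). With A = F = 2.5, the formula in Step 1 gives about 222 events by month 60 at 5% withdrawal per year and about 205 at 10%.
- **Blinding limits bias.** Loss that differs by arm is less likely in a double-blind trial. This stands, but blinding does not exclude it, because recurrence itself may prompt other therapy or missed visits, and the treatment may change recurrence.
- **Other therapy may be rare.** It is prohibited before recurrence in the Target Population, and no frequency is given. That limits the size of this half but does not resolve the conflict between sections.

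**Conclusion.** The point holds as a design improvement of moderate weight. Sections 4.3 and 6.7.2 create avoidable censoring in patients who consent and could still be assessed, and they conflict with Section 3.1 and with the structure of the sensitivity analyses. The avoidable loss is about 0.5 to 12 events of the planned 208 at month 48. That range rests on assumed withdrawal of 2% to 10% per year, an assumed recoverable share of 10% to 50%, exponential recurrence times and uniform accrual. Power is largely protected by the event-driven design. What remains is possible bias, mainly if loss differs by arm, and an undefined status for withdrawn patients in the 2-Year Recurrence Rate. The documents contain no evidence that such bias occurred.

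A reader might also infer that the trial's reported results are affected. They are not: the SAP removed all efficacy endpoints and sensitivity analyses after early termination, so this concerns the protocol's design only.

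**What to change.** - In Section 4.3, remove two missed cystoscopies as a compulsory withdrawal reason. Reserve loss to follow-up for patients who cannot be contacted or assessed. Keep the others on the scheduled cystoscopies and count the first confirmed recurrence whenever it is found.
- Reconcile Section 3.1 with the synopsis and Section 6.7.2 on whether other bladder cancer therapy ends follow-up. For patients who start such therapy, keep recording cystoscopy and pathology outcomes as data collection only, with no change to what treatment is permitted. Prespecify censoring at the start of that therapy as one analysis.
- In Section 8.5.6.1, state how withdrawn patients enter the 2-Year Recurrence Rate.
- Leave the other withdrawal reasons as they are, including non-target histology, adverse event, refusal, consent withdrawal, pregnancy, cystectomy and death.

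The cost is protocol wording and a few further visits that are already on the schedule.
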